## **5.2 Treatment Period**

Subjects eligible after completing all screening evaluations will be randomly assigned in a 1:1 fashion ([Section 3.4](#)) to receive either cabozantinib in combination with nivolumab and ipilimumab or cabozantinib-matched placebo in combination with nivolumab and ipilimumab ([Section 6.1.1](#)). Subjects should receive their first dose of study treatment within 3 days after randomization.

While the subject is receiving study treatment, the subject's clinical status is to be evaluated by an Investigator at each clinic visit to confirm that the subject is suitable for continuing study treatment and to make timely decisions regarding any reduction (cabozantinib/placebo only), interruption, or restarting of study treatment. Clinical laboratory results from samples obtained during clinic visits and tumor assessments from imaging visits are to be reviewed by an Investigator

Subjects will receive study treatment as long as they continue to experience clinical benefit in the opinion of the Investigator or until unacceptable toxicity, the need for subsequent systemic anti-cancer treatment, or until any other reasons for treatment discontinuation listed in the protocol ([Section 3.6](#)). Study treatment may continue after radiographic progression per RECIST 1.1 as long as the Investigator believes that the subject is still receiving clinical benefit from study treatment and that the potential benefit of continuing study treatment outweighs potential risks ([Section 5.7.6.2](#)). Crossover between treatment arms will not be allowed.

Study completion is defined in [Section 3.6.3](#).

CONFIDENTIAL

Protocol XL184-313 Protocol Amendment 3.0  
Page 62 of 193

Safety will be assessed on the date of the first dose (W1D1) and every 3 weeks (W4D1, W7D1, W10D1), and then every 4 weeks thereafter (W14D1, W18D1, W22D1 etc). Additional evaluations of hematology, serum chemistry, and urinalysis will be performed at W3D1, W6D1, W9D1, and W12D1. Safety follow-up visits will be performed 30 (+14) days (FU-1 visit) and approximately 100 ( $\pm$ 14) days (FU-2 visit) after the date of the decision to permanently discontinue study treatment (see [Section 5.4](#)). All post-randomization safety laboratory tests may be assessed by local laboratories.

If study treatment is held due to AEs, investigators should perform additional safety assessments weekly (or more frequently as clinically indicated).

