#### **9.4.1 Adverse Events**

Adverse event terms recorded on the CRFs will be mapped to preferred terms using the Medical Dictionary for Regulatory Activities (MedDRA). The Investigator will classify the severity of AEs using the CTCAE v5 and will judge each event to be “not related” or “related” to study treatment.

A treatment emergent adverse event (TEAE) is defined as any event that begins or worsens on or after date of first dose of study treatment. Only TEAEs with an onset date prior to date of decision for treatment discontinuation (the later of the date of the decision of the Investigator to permanently discontinue study treatment or the date of the last dose of study treatment taken by

CONFIDENTIAL

the subject) + 30 days (+ 100 days for SAEs and certain other AEs; [Section 8.3](#)) will be tabulated in summary tables.

The frequency and percentage of subjects with TEAEs will be tabulated for overall incidence by system organ class and/or preferred term by treatment arm. Related TEAEs, serious TEAEs, related serious TEAEs, high-grade TEAEs, Grade 5 TEAEs, and TEAEs resulting in study treatment discontinuation will be similarly summarized. Summaries by worst reported severity for each event within a subject will also be provided.

At each level of summarization, a subject will be counted only once for each AE preferred term he/she experiences within that level (ie, multiple episodes of events with the same preferred terms will be counted only once).

All reported subject deaths will be summarized by treatment group, cause of death, and relationship to study treatment.

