### **9.5           Power and Sample Size**

The study is designed to provide adequate power for both PFS and OS. A larger sample size is needed to provide reasonable power for OS than for PFS. As a result, if PFS is evaluated in the entire study sample, the PFS events may be biased toward shorter progression times. Thus, to allow longer, more robust PFS follow up among a fewer number of subjects this study employs a “trial within a trial design.” The primary analysis of PFS will be conducted after at least 249 PFS events have been observed among the first 440 randomized subjects, defined as the PFS Intent-to-Treat (PITT) population.

CONFIDENTIAL

Protocol XL184-313 Protocol Amendment 3.0  
Page 129 of 193

For PFS, a total of 249 events in the first 440 randomized subjects provides the study with 90% power for a 2-sided log-rank test with a 5% level of significance to detect a HR of 0.66.

Assuming an exponential distribution of PFS, this corresponds with a 52% increase in median PFS from 11.6 months to 17.6 months. In the current design, the minimum observed effect that would result in statistical significance for PFS is a HR of 0.78, a 28% improvement in median from 11.6 to 14.9 months. Interim analysis of PFS is not planned.

For OS, the study was originally designed as follows: a total of 342 deaths among 676 randomized subjects are required to provide 90% power to reject the null hypothesis of no difference in OS using the log-rank test, a 2-sided significance level of 5%, three planned interim analyses (see Section 9.6), and assuming a true HR of 0.70. Assuming an exponential distribution for OS, this corresponds to a 43% improvement in median survival from 41 months to 58.6 months. Under this design, the minimum observed effect that would result in statistical significance for the final analysis of OS is an HR of 0.80, a 25% improvement in median from 41 to 51.1 months; a minimum difference in observed medians of approximately 10 months.

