## **2.4. Power and Sample Size Justification**

The study is designed to provide adequate power for analyses of both endpoints of PFS and OS for comparing the experimental arm with the control arm. A larger sample size is needed to provide reasonable power for OS than is required to evaluate PFS. As a result, if PFS were to be

evaluated in the entire study sample, the PFS events may be biased toward shorter progression times. Thus, to allow longer, more robust PFS follow up among a smaller number of subjects, this study employs a “trial within a trial design” (Hessel et al 2016).

The total sample size is 840 subjects, to be randomized in a 1:1 ratio to the experimental and control arms.

The futility analysis will be conducted when at least 100 events have been observed and analysis of primary endpoint of PFS will be conducted when at least 249 events have been observed in the first 440 subjects randomized. This will provide the study with 90% power to reject the null hypothesis of no difference in the survival function of PFS between the two study treatment arms with a 2-sided log-rank test at a 5% level of significance and assuming a true hazard ratio (HR) of 0.66. Assuming an exponential distribution of PFS, this corresponds with a 52% increase in median PFS from 11.6 months to 17.6 months. The minimum observed effect that would result in statistical significance for PFS is an HR of 0.78, a 28% improvement in median from 11.6 to 14.9 months.

As per a provision pre-specified in the protocol, the sample size for determining the primary endpoint (PFS Intent-to-Treat [PITT] population) may be expanded by 25% from the first 440 to first 550 randomized if a review of the accumulating PFS events data suggests that the 249 events required for the analysis will not be reached due to censoring caused by a higher than expected study drop-out or non-compliance stemming from the COVID-19 pandemic. The number of events targeted to perform this event-driven analysis will not change, thus such an increase would have no impact on study power, Type 1 error, criteria for statistical significance or the minimum effect size that rejects the null hypothesis. Version 3.0 of the SAP invoked this provision as described in [Section 4.8.1](#).

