### **4.5.1. Standard Period**

The standard safety observation period is the interval from the first dose date of study treatment to the earliest of:

- Date of last dose of last component of study treatment + 30 days, or
- Date of death, or
- Date subject withdrew consent for non-interventional study assessments, or
- Data cutoff date for analysis under consideration.

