#### **7.5.10. Health Care Resource Utilization**

For this study the following health care resource utilization (HCRU) parameters collected during the study observation period will be summarized for subjects in the ITT population:

- Days of hospitalization due to SAEs
- Days in intensive care unit (ICU) due to SAEs
- Number of emergency room (ER) visits due to SAEs
- Number and type of surgeries
- Number and type of transfusions

The summaries will include:

- Number and percentage of subjects in each category of HCRU
- Descriptive statistics for each HCRU category amongst those subjects who utilized the respective resource
- Total number of days or visits as applicable for each HCRU
- Per person year summary for each HCRU

To calculate the per person year value for a subject for a HCRU parameter, the numerator is the sum of the days or visits for that subject for the parameter; and the denominator is defined as:  $(\text{safety observation period} - \text{date of randomization} + 1) / 365.25$ .

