**Table 15: Adverse Event Summaries**

TEAE Included	Displays Sorted By	Format
Subject Incidence per SOC and PT by Severity		
All AEs	SOC and PT (MedDRA standard)	Worst severity: Any Grade, Grade 3-4, Grade 4, Grade 5
Events with An Incidence of $\geq 5\%$ (Any Grade) or $\geq 2\%$ (Grade 3-4) in either arm	SOC and PT (SOC per MedDRA standard, PT Within SOC by Decreasing Difference In Percent For Any Grade)	Worst severity: Any Grade, Grade 3-4, Grade 4, Grade 5
Events with An Incidence In The C+N+I Arm of $\geq 5\%$ (Any Grade) or $\geq 2\%$ (Grade 3-4) compared to control arm	SOC and PT (SOC per MedDRA standard, PT Within SOC by Decreasing Difference In Percent For Any Grade)	Worst severity: Any Grade, Grade 3-4, Grade 4, Grade 5
Subject Incidence of Non-Serious Adverse Event with An Increase of $\geq 5\%$ (Any Grade) in any arm	SOC and PT (SOC per MedDRA standard, PT Within SOC by Decreasing Difference In Percent For Any Grade)	Worst severity: Any Grade, Grade 3-4, Grade 4, Grade 5
Related AEs	SOC and PT (MedDRA standard)	Worst severity: Any Grade, Grade 3-4, Grade 4, Grade 5
SAEs	SOC and PT (MedDRA standard)	Worst severity: Any Grade, Grade 3-4, Grade 4, Grade 5
Related SAEs	SOC and PT (MedDRA standard)	Worst severity: Any Grade, Grade 3-4, Grade 4, Grade 5
Subject Incidence per PT and Severity		
All AEs	PT (Descending Freq. of Any Grade) PT (Descending Frequency of Grade 3-4) PT (Descending Freq. of Difference in Percent Between The Two Arms for Any Grades) PT (Descending Frequency of Difference in Percent Between The Two Arms for Grade3-4)	Worst severity: Any Grade, Grade 3-4, Grade 4, Grade 5
All AEs	PT (Descending Frequency of Difference in Any Grade)	Worst severity: Any Grade Odds-ratio, Relative Risk and Risk Difference
All AEs (for label)	PT (Descending Frequency of Any Grade)	Worst severity: Any Grade, Grade 1, Grade2, Grade 3, Grade 4, Grade 5
Related AEs	PT (Descending Frequency of Any Grade) PT (Descending Frequency of Grade 3-4)	Worst severity: Any Grade, Grade 3-4, Grade 4, Grade 5
SAEs	PT (Descending Frequency of Any Grade)	Worst severity: Any Grade, Grade 3-4, Grade 4, Grade 5
Related SAEs	PT (Descending Frequency of Any Grade)	Worst severity: Any Grade, Grade 3-4, Grade 4, Grade 5
Leading to Treatment Modifications and Discontinuations		

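### The between-arm AE ratios in SAP Table 15 rest on crude incidence in a treatment-dependent window, with no exposure-based companion

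*SAP*

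**What the plan says.** SAP Table 15 lists AE summaries as subject incidence. One row covering all AEs by preferred term, ordered by the between-arm difference, has the format "Worst severity: Any Grade Odds-ratio, Relative Risk and Risk Difference". Seven Grade 5 rows further down carry the same three measures. Six of these are bounded at 30 or 100 days after last dose, and one, for treatment-related deaths, has no bound. The protocol sets the same basis in Section 9.4.1: "The frequency and percentage of subjects with TEAEs will be tabulated for overall incidence".

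For the all-AE row the default window is the standard safety observation period of SAP 4.5.1. It starts at first dose and ends at the earliest of "Date of last dose of last component of study treatment + 30 days, or" death, withdrawal of consent for non-interventional assessments, or data cutoff. Protocol 5.2 sets how long treatment lasts: "Subjects will receive study treatment as long as they continue to experience clinical benefit in the opinion of the Investigator or until unacceptable toxicity". Protocol 3.6.1 lets one component continue after another stops, so stopping a single drug does not close the window.

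The design assumes that the arms differ in time to progression. SAP 2.4 says of the assumed hazard ratio that "this corresponds with a 52% increase in median PFS from 11.6 months to 17.6 months". A person-time scale appears once in the SAP, in 7.5.10: "Per person year summary for each HCRU". No AE table uses one.

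**The concern.** A crude proportion counts a subject as affected if the event occurs at any time while that subject is under observation. When one arm is observed longer, more of its subjects are affected even if the monthly rate is the same. If the triplet works as designed and subjects stay on it longer, its crude AE ratios rise above 1 without any increase in rate. If triplet subjects stop all treatment sooner because of toxicity, the ratios fall and real harm is understated. A reader of the printed ratios cannot tell which has happened. At stake is the descriptive reading of cabozantinib's added toxicity, chiefly for late or continuing events. No efficacy conclusion or type I error is affected.

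**Working it through.** **Inputs from the documents.** Median PFS is 11.6 and 17.6 months, exponential (SAP 2.4, Protocol 9.5). Accrual takes 21 months with a PFS cutoff at about 23 months (Protocol 9.5), so follow-up at that cutoff runs from about 2 to 23 months. Minimum follow-up in the first 550 randomized is 15.6 months (SAP 4.8.1). There are 420 subjects per arm.

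**Assumptions, not in the documents.** PFS stands in for time on treatment. The AE hazard is constant and equal in the two arms, at 0.005 to 0.10 per month unless stated. Longer follow-up is taken as 12 to 36 months, or as a fixed 15.6 or 24 months.

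**1. The plan's own figure.** Protocol 9.5 states "a total of 249 events in the first 440 randomized subjects" and "90% power for a 2-sided log-rank test with a 5% level of significance to detect a HR of 0.66". The Schoenfeld formula gives 4(1.960 + 1.282)² / (ln 0.66)² = 244 events and Freedman's gives 251, against 249 stated. The critical HR is exp(−2 × 1.960/√249) = 0.780, matching 0.78, and 11.6/17.6 = 0.659. The PFS assumption is internally consistent.

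**2. Fixed follow-up C, no 30-day tail.** P(AE) = h/(h + l) × [1 − exp(−(h + l)C)], where l = ln 2/11.6 = 0.0598 (control) or ln 2/17.6 = 0.0394 (triplet), and h is solved to give the stated control incidence. For C = 24 and 20% in control, h = 0.0185. The triplet value is then 0.0185/0.0579 × [1 − exp(−0.0579 × 24)] = 24.0%.

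| Follow-up | Control | Triplet | RR | OR |
|---|---|---|---|---|
| 15.6 months | 5% | 5.7% | 1.15 | 1.16 |
| 15.6 months | 20% | 22.8% | 1.14 | 1.18 |
| 24 months | 5% | 6.1% | 1.21 | 1.23 |
| 24 months | 20% | 24.0% | 1.20 | 1.26 |

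**3. Staggered entry with the 30-day tail, by numerical integration.**

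| Follow-up | Mean window, control vs triplet | RR, hazards 0.10 to 0.005 | Example at 0.02 per month |
|---|---|---|---|
| 2–23 months (planned) | 8.8 vs 9.8 months | 1.08 to 1.12 | 15.5% vs 17.2%, difference +1.7 points (SE 2.6) |
| 12–36 months (assumed) | 13.1 vs 15.7 months | 1.11 to 1.19 | 22.0% vs 25.8%, difference +3.8 points (SE 2.9) |

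At a hazard of 0.30 per month, where over 80% of subjects have the event, the RR is only 1.04 in both settings, but the OR is 1.23 and 1.47. The exposure-adjusted rate ratio is 1.00 in every constant-hazard case.

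**4. Early events.** With an equal hazard confined to the first 12 weeks, the crude RR is about 1.03 without the 30-day tail and 1.01 with it. The rate ratio is about 0.90 at 15.6 months and 0.85 at 24 months, below the true value of 1. If the early hazard is truly 1.2-fold higher on the triplet, the crude RR is about 1.2, while the rate ratio is about 1.08 to 1.10 at 15.6 months and 1.02 to 1.04 at 24 months.

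**5. Early stopping for toxicity.** An extra hazard of stopping all treatment on the triplet of 0.0598 − 0.0394 = 0.0204 per month, which is 1 − exp(−12 × 0.0204) = 22% per year, returns the crude RR to 1.00. At 0.04 per month it falls to 0.91 (planned follow-up, AE hazard 0.02).

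**The case against.** The strongest objection concerns the remedy. Person-time rates are not neutral either: step 4 shows that they hide early harm. The documents describe much of the expected toxicity as early. Protocol 6.6.3.1 puts most immune-related events in the first 12 weeks of exposure, and Protocol 6.6.2.1 lists hypertension, hand-foot syndrome and diarrhea among the early-onset events of cabozantinib. This stands, and it rules out reading AEs mainly from the rate ratio.

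Second, PFS is only a proxy. Treatment may continue past progression or stop for toxicity, and the expected 12 to 18 months on treatment is not given by arm. In an earlier study 9 of 44 triplet subjects (20.5%) had AEs leading to treatment discontinuation (Protocol 1.6). That text does not say how many stopped every component. This stands against any fixed direction of bias.

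Third, Protocol 9.4 and SAP 8 plan no formal safety comparison, and most Table 15 rows show incidence by grade only. This stands too: a reader might take these ratios for the trial's main safety contrast, but nothing in the documents gives them that role. It does not remove the point, since three effect measures will still be printed per preferred term.

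Fourth, exposure is summarized in SAP 6.5, and AESIs have time-to-onset summaries. This helps only in part. The exposure tables are not linked to incidence. SAP 8.4 limits time to onset to subjects with an event, while Appendix G also censors subjects without one, so that text needs reconciling. Other AEs have no such analysis.

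**Conclusion.** The point holds as a gap in a descriptive analysis. For the all-AE row, the crude OR, RR and RD depend on time at risk, and nothing planned separates that from event rate. Under the stated proxy and equal constant hazards, the distortion in RR is modest at the planned cutoff (about 1.08 to 1.12), larger with longer follow-up (about 1.1 to 1.2) and close to nil for events in the first 12 weeks.

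A reader might infer three stronger things that the documents do not support. One is that the crude ratios will make cabozantinib look more harmful than it is: the direction depends on exposure by arm, which is not stated and can reverse. Another is that the rate ratio should replace or outrank the crude ratio: for early-onset events it is the worse measure. The third is that every Grade 5 row shares the last-dose + 30-day window: those rows have their own windows, one of them unbounded.

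**What to change.** In SAP Table 15, keep the crude percentages and the OR, RR and RD, and add a companion in two places: the all-AE row that carries those measures, and the Grade 5 rows bounded at 30 or 100 days after last dose. The companion is either of these:

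- the exposure-adjusted incidence rate per arm (subjects with a first event divided by person-years at risk to first event or end of window), with a rate ratio and 95% CI; or
- cumulative incidence by arm, with death as a competing event.

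Person-time must match each row's own window. The unbounded Grade 5 row is left as it is.

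Add a reading note: the rate ratio informs late or continuing events. For early-onset events it is diluted by later event-free person-time, so the crude measure, or cumulative incidence at a fixed time, should be read. The rate ratio does not take priority.

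The cost is SAP wording, one derivation from dates already collected and a few more columns. The rate ratio also brings a constant-rate assumption, which the reading note makes explicit.

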## 8.2. Deaths

All subject deaths (Grade 5 TEAEs) will be summarized for all subjects in the Safety population.

Deaths will be summarized as follows:

- Number of subjects who died
- Deaths  $\leq$  30 days after the date of receipt of the last dose of study treatment
- Deaths  $\leq$  100 days after the date of receipt of the last dose of study treatment

In addition, under each category causality to study disease will also be summarized.

All reported subject deaths will be listed.

## 8.3. Adverse Events of Special Interest

Adverse events of special interest (AESIs) consist of AEs potentially associated with immune checkpoint inhibitor (ICI) therapies, cases of potential drug induced liver injury (DILI) and suspected transmission of an infectious agent by the study treatment.

Specific AEs may be observed due to treatment with ICIs. Routine and early recognition and management of these events may mitigate severe toxicities. Hence the sponsor has defined a set of preferred terms that are grouped under various AESI categories that will provide a consistent, reproducible, and transparent compilation of safety information over time. The select preferred terms are revisited and updated periodically.

Analysis of potential DILI is discussed in [Section 8.7.2](#) and cases of transmission of infectious agent by study treatment, if any, will be discussed in patient narratives.

The following summaries will be provided for potential adverse events associated with treatment due to ICI therapies for subjects in the Safety population. These summaries will be for such AESIs collected up to 100 days since last dose of study treatment:

**Table 16: Adverse Event of Special Interest Summaries**

TEAE included	Row-levels (sorted by)	Columns
Subject Incidence by Group, Preferred Term and Severity		
All AESIs	AESI and PT (AESI, PT within AESI by descending frequency of Any Grade)	Worst severity: Any Grade, Grade 3-4, Grade 4, Grade 5
AESIs leading to dose reduction/delay: 
 
• Of at least one component
 
• Of all components due to the same AESI
 
• Oral components
 
• Of any infusion component
 
	AESI and PT (AESI, PT within AESI by descending frequency of Any Grade)	Worst severity: Any Grade, Grade 3-4, Grade 4, Grade 5
AESIs leading to discontinuation 
 
• Of at least one component
 
• Of all components due to the same AESI
 
• Oral components
 
• Of any infusion component
 
	AESI and PT (AESI, PT within AESI by descending frequency of Any Grade)	Worst severity: Any Grade, Grade 3-4, Grade 4, Grade 5
AESIs leading to initiation of immune-modulating medication	AESI and PT (AESI, PT within AESI by descending frequency of Grade 3-4)	Worst severity: Any Grade, Grade 3-4, Grade 4, Grade 5
AESIs leading to initiation of high dose (defined in Section 6.4 ) of immune-modulating medication	AESI and PT (AESI, PT within AESI by descending frequency of Grade 3-4)	Worst severity: Any Grade, Grade 3-4, Grade 4, Grade 5
AESIs leading to initiation of immune-modulating medication and any infusion treatment discontinuation	AESI and PT (AESI, PT within AESI by descending frequency Grade 3-4)	Worst severity: Any Grade, Grade 3-4, Grade 4, Grade 5
All serious AESIs	AESI and PT (AESI, PT within AESI by descending frequency of Any Grade)	Worst severity: Any Grade, Grade 3-4, Grade 4, Grade 5
Serious AESIs leading to initiation of immune-modulating medication	AESI and PT (AESI, PT within AESI by descending frequency of Grade 3-4)	Worst severity: Any Grade, Grade 3-4, Grade 4, Grade 5
Serious AESIs leading to initiation of high dose (defined in Section 6.4 ) of corticosteroids	AESI and PT (AESI, PT within AESI by descending frequency of Grade 3-4)	Worst severity: Any Grade, Grade 3-4, Grade 4, Grade 5
Time to Onset of Event		
AESIs	Time to first onset of AESIs by Group Term	Any Grade, Grade 3-5
AESIs leading to initiation of immune-modulating medication	Time to first onset of AESIs by Group Term	Any Grade, Grade 3-5

TEAE included	Row-levels (sorted by)	Columns
AESIs leading to initiation of high-dose corticosteroids	Time to first onset of AESIs by Group Term	Any Grade, Grade 3-5
Time to Resolution		
AESIs	Time to Resolution by Group Term	Any Grade, Grade 3-5
AESIs leading to initiation of immune-modulating medication (choose the interval for the longest PT)	Time to Resolution by Group Term	Any Grade, Grade 3-5
AESIs leading to initiation of high-dose corticosteroids (choose the interval for the longest select PT)	Time to Resolution of AESIs by Group Term	Any Grade, Grade 3-5
Recur-after-Rechallenge		
AESIs	Group Term	Any Grade, Grade 3-5
AESIs leading to initiation of immune-modulating medication	Group Term	Any Grade, Grade 3-5
AESIs leading to initiation of high-dose corticosteroids	Group Term	Any Grade, Grade 3-5
Liver test abnormalities (laboratory data) ALT or AST > 3 x ULN ALT or AST > 10 x ULN		

